## 15.6. PREGNANCIES

A listing of all pre-treatment on-treatment and post-treatment pregnancies will be listed for ENR (including participants who enrolled more than once).

---

Document:

Author:

Version Number:

2.0

Version Date:

23APR2024

Template No.: CS\_TP\_BS016 Revision 6

Reference: CS\_WI\_BS005

Effective Date: 02Dec2019

Copyright © 2009, 2010, 2012, 2016, 2018, 2019 [REDACTED]. All rights reserved. The contents of this document are confidential and proprietary to [REDACTED] and its subsidiaries. Unauthorized use, disclosure or reproduction is strictly prohibited.

## 16. APPENDIX A

### 16.1. ALGORITHM FOR TREATMENT EMERGENCE OF ADVERSE EVENTS:

---

Document:

Author:

Version Number:

2.0

Version Date:

23APR2024

Template No.: CS\_TP\_BS016 Revision 6

Reference: CS\_WI\_BS005

Effective Date: 02Dec2019

Copyright © 2009, 2010, 2012, 2016, 2018, 2019 [REDACTED]. All rights reserved. The contents of this document are confidential and proprietary to [REDACTED] and its subsidiaries. Unauthorized use, disclosure or reproduction is strictly prohibited.

AE START DATE	AE STOP DATE	ACTION
Known	Known/Partial/ Missing	
If AE stop date is partial, impute AE stop date as latest possible date (i.e., last day of month if day unknown or 31st December if day and month are unknown).
 
If AE start date < study treatment start date, assign as pre-treatment AE.
 
If AE start date >= study treatment start date and <= study treatment stop date + 14 days, assign as TEAE.
 
If AE start date > study treatment stop date + 14 days, assign as post-treatment AE.

Partial	Known/Partial/ Missing	
If AE stop date is partial, impute AE stop date as latest possible date (i.e., last day of month if day unknown or 31st December if day and month are unknown).
 
Impute AE start date as the study treatment start date, if:
 

the year of the AE start date is equal to the year of the study treatment start date and the AE stop date is later or equal to the study treatment start date or is missing.

the year and month of the AE start date is equal to the year and month of the study treatment start date and the AE stop date is later or equal to the study treatment start date or is missing.

 
Otherwise, Impute AE start date as earliest possible date (i.e. first day of month if day unknown or 1st January if day and month are unknown). Then:
 
If AE start date < study treatment start date, assign as pre-treatment AE.
 
If AE start date >= study treatment start date and <= study treatment stop date + 14 days, assign as TEAE.
 
If AE start date > study treatment stop date + 14 days, assign as post-treatment AE.

Document: [REDACTED]

Author: [REDACTED]

Version Number:

2.0

Version Date:

23APR2024

Template No.: CS\_TP\_BS016 Revision 6

Reference: CS\_WI\_BS005

Effective Date: 02Dec2019

Copyright © 2009, 2010, 2012, 2016, 2018, 2019 [REDACTED] All rights reserved. The contents of this document are confidential and proprietary to [REDACTED] and its subsidiaries. Unauthorized use, disclosure or reproduction is strictly prohibited.

AE START DATE	AE STOP DATE	ACTION
Missing	Known	If AE stop date < study treatment start date, assign as pre-treatment AE If AE stop date >= study treatment start date, assign as TEAE
	Partial	Impute AE stop date as latest possible date (i.e., last day of month if day unknown or 31st December if day and month are unknown), then: If AE stop date < study treatment start date, assign as pre-treatment AE If AE stop date >= study treatment start date assign as TEAE If AE stop date >= study treatment stop date + 14 days, then post-treatment
	Missing	Assumed as TEAE

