Partial	Known/Partial/Missing	
If stop date is partial, impute stop date as latest possible date (i.e., last day of month if day unknown or 31st December if day and month are unknown).
 
Impute start date as the study treatment start date, if:
 

the year of the start date is equal to the year of the study treatment start date and the stop date is later or equal to the study treatment start date or is missing.

the year and month of the start date is equal to the year and month of the study treatment start date and the stop date is later or equal to the study treatment start date or is missing.

 
Otherwise, impute start date as earliest possible date (i.e. first day of month if day unknown or 1st January if day and month are unknown). Then:
 
If start date < study treatment date, assign as prior.
 
If start date <math>\geq</math> study treatment start date and start date <math>\leq</math> end of treatment + 7 days, assign as concomitant except medications for contraceptive use.
 
If start date <math>></math> end of treatment + 7 days, assign as post study. For all medications for contraceptive use, if start date <math>></math> end of treatment, assign as post study.

Document: [REDACTED]

Author: [REDACTED]

Version Number:

2.0

Version Date:

23APR2024

Template No.: CS\_TP\_BS016 Revision 6

Reference: CS\_WI\_BS005

Effective Date: 02Dec2019

Copyright © 2009, 2010, 2012, 2016, 2018, 2019 [REDACTED]. All rights reserved. The contents of this document are confidential and proprietary to [REDACTED] and its subsidiaries. Unauthorized use, disclosure or reproduction is strictly prohibited.

Medication START DATE	Medication STOP DATE	ACTION
Missing	Known	If stop date < study treatment start date, assign as prior If stop date >= study treatment start date, assign as concomitant
	Partial	Impute stop date as latest possible date (i.e. last day of month if day unknown or 31st December if day and month are unknown), then: If stop date < study treatment start date, assign as prior If stop date >= study treatment start date, assign as concomitant
	Missing	Assign as concomitant

---

Document: [REDACTED]

Author: [REDACTED]

Version Number:

2.0

Version Date:

23APR2024

Template No.: CS\_TP\_BS016 Revision 6

Reference: CS\_WI\_BS005

Effective Date: 02Dec2019

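### The year-match bullet in SAP 16.1 is not limited to dates with the month unknown, so some AEs whose recorded month places them outside treatment become Day 1 TEAEs

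*SAP*

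**What the plan says.** SAP 16.1 has one row for every partial AE start date, whether only the day is missing or the day and month are both missing. The instruction is "Impute AE start date as the study treatment start date, if" either of two bullets is met:

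- Bullet 1: "the year of the AE start date is equal to the year of the study treatment start date".
- Bullet 2: "the year and month of the AE start date is equal to the year and month of the study treatment start date".

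Each bullet also carries the same further condition on when the event ended: "the AE stop date is later or equal to the study treatment start date or is missing". A partial stop date is first set to its latest possible date. If neither bullet is met, the fallback applies: "Otherwise, Impute AE start date as earliest possible date", explained as "first day of month if day unknown or 1st January if day and month are unknown". The resulting date is then classified: "If AE start date >= study treatment start date and <= study treatment stop date + 14 days, assign as TEAE". Earlier dates are pre-treatment and later dates are post-treatment.

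SAP 15.1 gives the governing principle. An AE takes the worst-case class (treatment-emergent) when a partial start date makes its status impossible to determine, and pre-treatment AEs are kept out of the TEAE analyses. SAP 12 states the same principle for medications. SAP 16.2 repeats the structure for medications, beginning with "the year of the start date is equal to the year of the study treatment start date".

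**The concern.** Bullet 1 looks only at the year and the stop date. Any date that meets bullet 2 already meets bullet 1, so bullet 2 does no work. In a matching year, the first-of-month fallback is reached only when the AE stopped before first dose. A programmer who follows the table literally will discard a recorded month that settles the classification.

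Safety is now the only analysis (SAP 2 and 3.2), and the proportion of participants with an AE is a primary endpoint in SAP Table A. The rule feeds that numerator directly. Early termination also matters. The shorter the treatment, the more likely it is that the weeks after the last tablet fall in the same calendar year as first dose, which is what the post-treatment error needs.

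**Working it through.** The plan gives no figure for this rule, so there is none to reproduce. The check applies the rule as written and compares it with the same rule after bullet 1 is limited to dates with the month unknown.

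**Logic.** Let S mean that the stop date is on or after first dose, or missing. Bullet 1 is (year matches and S). Bullet 2 is (year and month match and S). Bullet 2 implies bullet 1, so (bullet 1 or bullet 2) reduces to bullet 1.

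**Worked cases.** The dates are illustrative and not from the documents: first dose 15 Jun 2022, last dose 10 Aug 2022, so last dose + 14 days is 24 Aug 2022.

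| Recorded start | Stop | As written | Bullet 1 limited |
|---|---|---|---|
| May 2022 | missing | 15 Jun, TEAE | 1 May, pre-treatment |
| May 2022 | 20 Jun 2022 | 15 Jun, TEAE | 1 May, pre-treatment |
| May 2022 | Jun 2022 (set to 30 Jun) | 15 Jun, TEAE | 1 May, pre-treatment |
| May 2022 | 31 May 2022 | 1 May, pre-treatment | unchanged |
| Jun 2022 | missing | 15 Jun, TEAE | unchanged |
| Jul 2022 | 20 Jul 2022 | 15 Jun, TEAE | 1 Jul, TEAE |
| Sep 2022 | missing, or 5 Oct 2022 | 15 Jun, TEAE | 1 Sep, post-treatment |
| 2022, month unknown | missing | 15 Jun, TEAE | unchanged |
| Dec 2021 | missing | 1 Dec 2021, pre-treatment | unchanged |

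The May case is realistic. Six weeks before 15 June is 4 May, so an onset on 4 to 31 May fits the maximum Pre-treatment Period. The September case shows only the mechanism: V7 falls 14 to 19 days after last intake (Protocol 8.4.1), here 24 to 29 August, so September lies beyond routine collection.

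**How often the rule misfires, given a day-missing date.** Assumptions: first dose spread evenly over a 365-day year, onsets spread evenly, day missing, stop date missing.

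- Before treatment: 365 × 42 = 15,330 pairs of first-dose date and onset 1 to 42 days earlier. In 9,957 the recorded month ends before first dose. Of these, 9,054 (9,054/9,957 = 91%) become Day 1 TEAEs. The other 903 fall in the previous calendar year and escape.
- After treatment: 365 × 5 = 1,825 pairs with onset 15 to 19 days after last dose. In only 180 (180/1,825 = 10%) does the recorded month begin after last dose + 14 days. Of those 180, the number that become Day 1 TEAEs is 150 (83%) for 28 days of treatment, 120 (67%) for 84 days, 75 (42%) for 168 days and 0 for 364 days.
- With bullet 1 limited, both error counts are zero.

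**Medications, same dates.** A drug recorded as started in January 2022 and still taken is moved to 15 June and listed as concomitant, although SAP 12 defines prior as started before first dose. A post-study contraceptive recorded as started in September 2022 is also moved to 15 June. It is then not prior, is excepted from concomitant in 16.2, and does not start after end of treatment, so 16.2 gives it no class. The worst-case default in SAP 12 would call it concomitant, although its month shows it to be post-treatment.

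**The case against.** The best defence is that the intention is plain. The same table cell separates day unknown from day and month unknown, the two bullets follow that split, and only the literal reading makes bullet 2 redundant. That is probably what the authors meant. The text does not say it, however, and a table headed as an algorithm will be programmed as written.

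SAP 6.2 offers a second defence: AEs commencing on the first-dose date are classed by an eCRF assessment of whether they began before treatment. The SAP does not say that this applies to imputed dates, and it cannot help post-treatment onsets.

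The arguments about size are stronger and largely stand:

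- The stop-date condition protects AEs that ended before first dose. A reader might infer that every partially dated AE in the first-dose year is pulled to Day 1 and misclassified; the documents do not support that.
- AE collection runs from consent, with a Pre-treatment Period of at most 6 weeks, to V7. Onsets many months either side of treatment would not routinely be in the AE data. After V7, Protocol 8.4.1 requires only SAEs considered related to be reported.
- Protocol Table 8 narrows pre-treatment AE reporting to events due to a protocol procedure or causing exclusion, although the text of 8.4.1 asks for all AEs from consent. If sites follow the table, few pre-treatment AEs are eligible.
- A reader might also infer that moving an onset within treatment to Day 1 distorts results. SAP 15.1 plans incidence summaries and no time-to-onset analysis, so that shift changes no planned summary. SAP 12 plans only listings of medications.
- The study has one arm and no statistical tests, and the error counts too many TEAEs rather than too few. That limits the harm, but SAP 15.1 confines its own conservatism to AEs that cannot be placed.

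**Conclusion.** The rule as written gives a wrong class to a definable set of AEs: month known, year equal to the first-dose year, stop date on or after first dose or missing, and the recorded month wholly before first dose or wholly after last dose + 14 days. That contradicts SAP 15.1. In 16.2 the same wording mislabels some prior drugs and can leave a post-study contraceptive unclassified.

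The practical effect is probably small. The number of AEs with a missing day is not given, and neither are actual treatment durations. The 91% and the 83% to 0% figures are conditional on a day-missing, stop-missing date whose month is already decisive, under even spread. They are not estimates of how many AEs are affected, and the documents do not support a claim that the reported AE proportions are materially inflated. The correction is still worth making, because a stated rule yields a wrong class and is easily repaired.

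**What to change.** In SAP 16.1 and 16.2:

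- limit the year bullet to dates with day and month both unknown;
- limit the year-and-month bullet to dates with only the day unknown;
- let every other known month fall to the existing earliest-possible-date rule.

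Dates that are truly ambiguous still become Day 1 TEAEs, so the worst-case principle is kept where SAP 15.1 intends it.

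This does not cover one case in 16.2. A contraceptive recorded as starting in the same month as the last tablet (for example August 2022 with last tablet 10 August) is set to 1 August, which is not after end of treatment, and stays unclassified. One added line in 16.2 should say how it is classed.

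The cost is a clause in each bullet of two tables and a small programming edit. No new data are needed. A count of AEs and medications with partial start dates, and of those whose class changes, would show whether the correction affects any reported number.

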9.4.3 Safety Analysis

The APaT population will be used for all safety analyses.

Safety and tolerability will be assessed by clinical review of all relevant parameters including AEs, laboratory values, vital signs, and body weight.

For the analysis of safety data, the following conventions will be used:

- Baseline will be defined as the last measurement before the first study drug intake.
- The on-treatment period will be defined as the period from the day of first tablet intake up to and including the day of last active study drug intake, extended by 14 days. However, any delayed events or diagnoses judged by the Investigator to be related to study drug will also be considered to have occurred on-treatment and will be included in the safety analysis.
- Last measurement is the last value obtained during the on-treatment period.

The proportion of participants with prespecified events listed as ECIs described in Section 8.4.5 during the on-treatment period will be provided along with corresponding 95% Clopper-Pearson CIs. All ECIs will be summarized, even if the incidence is zero.

In addition, the broad AE categories consisting of the percentage of participants with any AE, a drug-related AE, a serious AE, an AE, which is both drug-related and serious, and who discontinued study drug due to an AE will be summarized with corresponding 95% Clopper-Pearson CIs (Table 10). On-treatment AEs are those occurring from first intake of study drug to 14 days after intake of the last active tablet of study drug. AEs occurring during the designated pre-treatment (between V1 and first intake of study drug) and post-treatment (>14 days after last tablet intake of study drug) periods will be provided.

Table 10 Analysis Strategy for Safety Parameters

Safety Endpoint ^a	Within Group 95% CI ^b	Descriptive Statistics
Any AE	X	X
Any Serious AE	X	X
Any Drug-Related AE	X	X
Any Serious and Drug-Related AE	X	X
Discontinuation due to AE	X	X
Specific AEs, SOCs, ECIs, and PDLCs (incidence ≥ 4 participants)		X
Specific AEs, SOCs, ECIs, and PDLCs (incidence < 4 participants)		X
Change from Baseline Results (laboratory tests, vital signs)		X

Abbreviations: AE=adverse event; CI=confidence interval; ECI=event of clinical interest; PDLC=Predefined Limit of Change; SOC=System Organ Class; X=results will be provided.

a. AE references refer to both clinical and laboratory AEs.

b. 95% CIs will be calculated using the Clopper-Pearson method.

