For continuous measures such as changes from baseline in laboratory tests and vital sign parameters, summary statistics for on-treatment values will be provided in table format at V2 and V7.

For summary statistics of laboratory parameters and vital signs per visit, visit windows as described in [Table 11](#) will be used.

Table 11 Timeframe Used in the Analysis of Vital Signs and Laboratory Parameters

Definition	Visit	Visit window (treatment day)
Baseline	V1 Screening	<1
In-treatment ^a	V3 After Cycle 1	29 \pm 28 days
	V4 After Cycle 4	113 \pm 28 days
	V5 After Cycle 7	197 \pm 28 days
	V6 After Cycle 10	281 \pm 28 days
	V7 After Cycle 13	379 \pm 28 days
	Last measurement	>1

Abbreviation: V=Visit

a. From Day 1 until ≤ 28 days after last tablet intake; Day 1 is defined as day of first study drug intake

Values outside these visit windows, or outside the defined in-treatment period for post-baseline assessments, will be excluded from the analysis of that particular visit.

However, these visit windows will only be applied for analyses performed per visit; no values will be excluded from the determination of markedly abnormal laboratory or vital signs values

(unless outside the defined in-treatment period). If more than one observation is available within a specific visit window, the latest value will be used for analysis.

9.4.3.1 *Adverse Events*

An overview table of the number (percentage) of participants with any AEs, SAE, drug-related AEs, any serious drug-related AEs, any discontinuation due to AE, any discontinuation due to a SAE, any discontinuation due to a drug-related AE, any discontinuation due to serious drug-related AE, and any deaths will be presented for the on-treatment period. Pre-treatment AEs/SAEs starting before the in-treatment period will be excluded from the AE analyses (unless there is an increase in Investigator assessed intensity or causality, or the AE meets SAE criteria post-treatment allocation) and reported in separate frequency tables with the methods described above.

The number (percentage) of participants with at least one AE will be presented in a frequency table of Medical Dictionary for Regulatory Activities (MedDRA) system organ class (according to the primary path) and MedDRA preferred term. The same tables will be presented by relationship to study drug (“Related” and “Not related”) by the Investigator; and by severity of the AE (“mild”, “moderate”, “severe”).

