### 15.1. ADVERSE EVENTS

AEs will be coded using MedDRA coding dictionary, Version 26.1 or higher.

Treatment-emergent adverse events (TEAEs) are defined as AEs that started on or after the day of first dose of study treatment (or worsened in severity) and prior to the last date of study treatment + 14 days (inclusive). See Appendix A for handling of partial dates for AEs. In the case where it is not possible to define an AE as treatment emergent or not due to a partial start date, the AE will be classified by the worst case; i.e. treatment emergent. Pre-treatment AEs/SAEs starting before the on-treatment period, including those starting on the day of first dose of study treatment yet prior to the study treatment intake, will be excluded from the TEAE analyses. Pre- and post-treatment AEs will be identified in listings.

---

Document: [REDACTED]

Author: [REDACTED]

Version Number:

2.0

Version Date:

23APR2024

Template No.: CS\_TP\_BS016 Revision 6

Reference: CS\_WI\_BS005

Effective Date: 02Dec2019

Copyright © 2009, 2010, 2012, 2016, 2018, 2019 [REDACTED]. All rights reserved. The contents of this document are confidential and proprietary to [REDACTED] and its subsidiaries. Unauthorized use, disclosure or reproduction is strictly prohibited.

An overview table of number (%) of participants within each of the categories described in the sub-section below will be provided as specified in the templates. The broad AE categories consisting of the percentage of participants with any TEAE, a drug-related TEAE, a serious TEAE, a TEAE that is both drug-related and serious, and a TEAE leading to discontinuation of study treatment will be summarized. Similar Table by BMI group ( $<30 \text{ kg/m}^2$ ,  $\geq 30 \text{ kg/m}^2$ ) will be provided. Listings will include all AEs (including participants who enrolled more than once).

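### SAP 16.1: for an adverse event with a missing start and a partial stop date, the post-treatment line fully overlaps the TEAE line and tests the stop date instead of onset

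*SAP*

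**What the plan says.** SAP 16.1 sorts adverse events into pre-treatment, TEAE and post-treatment according to which dates are known.

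- **Known or partial start:** the start date decides. An event is post-treatment only if its start (imputed where partial) is later than "study treatment stop date + 14 days, assign as post-treatment AE". A start on day 14 itself is a TEAE.
- **Missing start, known stop:** "If AE stop date >= study treatment start date, assign as TEAE". An earlier stop gives pre-treatment. There is no post-treatment outcome.
- **Missing start, missing stop:** TEAE.
- **Missing start, partial stop:** the stop is set to the last day of the month, or to 31 December. The same two outcomes follow as for a known stop, and then a third line: "If AE stop date >= study treatment stop date + 14 days, then post-treatment".

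The TEAE definition in SAP 15.1 opens with "AEs that started on or after the day of first dose of study treatment (or worsened in severity" and runs to last dose plus 14 days, inclusive. The same section sends events that cannot be classified because of a partial start date to the worst case, which it names as treatment-emergent.

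On related matters, protocol 9.4.3 says that "any delayed events or diagnoses judged by the Investigator to be related to study drug will also be considered to have occurred on-treatment". Protocol 9.4.3.1 excludes pre-treatment events "unless there is an increase in Investigator assessed intensity or causality, or the AE meets SAE criteria post-treatment allocation". SAP 15.1 has no counterpart to the first clause. Of the second, it keeps only worsening in severity.

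**The concern.** An event with a missing start and a partial stop can satisfy two lines of 16.1 that give different classes, and 16.1 does not say which prevails. If the later line prevails, a late stop is treated as evidence of a late onset, which it is not.

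The report is safety-only, and the serious-event and events-of-clinical-interest summaries (SAP 15.1.3 and 15.1.5) cover TEAEs only. An event labelled post-treatment therefore leaves those summaries and remains only in the listings. Whether it does so could depend on how a programmer orders two statements.

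**Working it through.** The plan gives no figure to reproduce. The check is of logic and calendar dates. Let F be the first-dose date, L the last-dose date and S the imputed stop date.

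**1. Overlap.** The TEAE line is S ≥ F. The post-treatment line is S ≥ L + 14. Since L ≥ F, L + 14 is always later than F, so S ≥ L + 14 implies S ≥ F. No event can meet the post-treatment line alone. An enumeration agrees: 365 last-dose dates in 2023 × 5 assumed exposure lengths (1, 28, 84, 182, 364 days) × 22 month-only stop months = 40,150 combinations. Of these, 13,760 meet the post-treatment line, and all 13,760 also meet the TEAE line.

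**2. Which date is tested.**

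| Row of SAP 16.1 | Condition for post-treatment |
|---|---|
| Known start | start > L + 14 |
| Partial start | imputed start > L + 14 |
| Missing start, known stop | none |
| Missing start, partial stop | imputed stop ≥ L + 14 |
| Missing start, missing stop | none |

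Only one row uses the stop date. Example: last dose 10 June 2023, so day 14 is 24 June. A missing start with a stop recorded as 30 June is a TEAE. If the stop is recorded only as June 2023, it is imputed to the same 30 June, yet the post-treatment line is now met. Less information has changed the class. The matching medication row in SAP 16.2 (missing start, partial stop) has no post-treatment outcome.

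**3. The boundary.** The line uses ≥, whereas SAP 15.1 and the rows with a start date count day 14 as TEAE. Example: last dose 17 July 2023, stop July 2023, imputed to 31 July = 17 + 14. The event ended by day 14 at the latest, so it cannot have started after day 14. This equality needs L to be 14 days before a month end, which gives one date per month, or 12 of 365. For year-only stops it arises on one date, 17 December.

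**4. Calendar reach of the line, if it prevails.** Last-dose dates in 2023 on which it is met:

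- Month-only stop in the last-dose month: last-dose day ≤ month length − 14. That is 7 × 17 + 4 × 16 + 1 × 14 = 197 (54%).
- Month-only stop in the following month: all 365.
- Year-only stop: last dose by 17 December, 365 − 14 = 351 (96%).

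On those dates, the mean share of possible stop days on or before L + 14, which would rule out a post-treatment onset, is 75%, 11% and 52% respectively. These figures weight every last-dose date and every possible stop day equally.

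**5. Clauses not carried over.** The protocol is not uniform on delayed related events. A later sentence of 9.4.3 reads "On-treatment AEs are those occurring from first intake of study drug to 14 days after intake of the last active tablet of study drug", without the exception, and 8.4.1 likewise gives a plain 14-day cutoff. SAP 6.5, 15.1 and 16.1 follow the plain cutoff. For pre-treatment events, SAP 15.1 says that those starting before the on-treatment period, including on the first-dose day "yet prior to the study treatment intake, will be excluded from the TEAE analyses", with no trigger for increased causality or for meeting SAE criteria. Protocol 9.4.3 counts its 14 days from the last active tablet in some sentences and from the last tablet in another. After a full blister these differ by 28 − 24 = 4 days. The SAP uses the last tablet. SAP 3.2 declares none of this for adverse events.

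**The case against.** **The worst-case rule in SAP 15.1 settles the ambiguity.** It points clearly to TEAE, and a programmer who applied it would ignore the disputed line. This narrows the problem but does not remove it: the rule is worded for partial start dates, not missing ones, and 16.1 contains an explicit line that contradicts it.

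**The line is rarely impossible.** This stands. Only the day-14 equality makes a post-treatment onset impossible: 12 of 365 last-dose dates for month-only stops, 1 for year-only. Elsewhere the event may indeed have begun after the window.

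**A reader might infer that 54%, 100% or 96% of such events are misclassified.** The documents do not support that. The percentages are calendar counts that follow from month lengths and the 14-day offset, and they apply only if the post-treatment line prevails. The documents do not say how many events have a missing start and a partial stop.

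**A reader might also infer that the SAP breaches the protocol by dropping the two clauses.** It does not. Protocol 9.4 says the SAP prevails where the two differ, and the protocol itself states the plain cutoff in two other places. SAP 3.2 is not wholly silent on the anchor either: it refers to the last tablet, though for laboratory and vital-sign data. What remains is non-declaration.

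**Conclusion.** The line in SAP 16.1 is wrong as written. It overlaps completely with the line before it, tests a late-imputed stop where the definition uses onset, and disagrees with 15.1 at day 14. The overlap holds for any treatment dates; the calendar counts assume last-dose dates in 2023.

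The consequence is minor. The study has one arm and no testing, the affected events are probably few, and every adverse event stays in the listings with pre- and post-treatment events identified.

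The clauses not carried over are a secondary, optional point about SAP 3.2. Their effect is also likely to be small. Protocol 8.4.1 places the final visit 14 to 19 days after last intake, so scheduled collection could add delayed related events from days 15 to 19 at most. Protocol Table 8 largely limits pre-treatment reports to events that are procedure-caused or cause exclusion, although the text of 8.4.1 is broader.

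The output templates that the SAP relies on were not available for this check, so a footnote there that sets an order between the lines cannot be ruled out.

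**What to change.** Delete the post-treatment line from the missing-start, partial-stop row of SAP 16.1, so that an imputed stop on or after first dose gives TEAE, as in the known-stop row. Changing ≥ to > would cure only the day-14 case and leave the overlap.

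The cost is one deleted line and a small program change. The downside is that a few events that truly began after the window may be counted as TEAEs, which is the direction SAP 15.1 already chooses for unclear cases.

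Optionally, add one sentence to SAP 3.2 stating that, for TEAEs, the SAP does not carry over the delayed-related-event clause of protocol 9.4.3 or the causality and SAE triggers of 9.4.3.1, and counts 14 days from the last tablet. Restoring the clauses is not needed to cure the fault.
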